It is possible that participants may be upset by a question in the interview or survey, although our prior experience using these questionnaires with patients who have knee osteoarthritis or low back pain have found that it is very rare for participants to be upset. Nevertheless, study staff will screen surveys for adverse events and address them as described in the next section.

There are no formal stopping rules for this minimal risk study.

Describe the plan to be followed by the Principal Investigator/study staff for review of adverse events experienced by subjects under his/her care, and when applicable, for review of sponsor safety reports and DSMB reports. Describe the plan for reporting adverse events to the sponsor and the Partners' IRB and, when applicable, for submitting sponsor safety reports and DSMB reports to the Partners' IRBs. When the investigator is also the sponsor of the IND/IDE, include the plan for reporting of adverse events to the FDA and, when applicable, to investigators at other sites.

NOTE: In addition to the adverse event reporting requirements of the sponsor, the principal investigator must follow the Partners Human Research Committee guidelines for Adverse Event Reporting

Any adverse event or patient complaint that occurs as a result of or related to this pilot project will be addressed immediately upon receiving it. We will also relay any such event to the Informed Medical Decisions Foundation if it pertains directly to the SDM program. Again, the Health Decision Sciences Center (HDSC) staff are available to address any questions or concerns that are received from the patients, either directly or through the

patients' clinician. We will keep records of any feedback, questions, concerns and/or complaints that are received, and we will address them immediately and appropriately.

The HDSC have clinical co-investigators in primary care and surgery who will be able to consult with study staff on any clinical issues that become apparent. For example, if patients raise a clinical issue with study staff during the course of phone reminders or on the written surveys. However, if a serious adverse event occurs relating to the study, then the principal investigator will report the event to the IRB within 24 hours and will file an HRC Adverse Event Form within 10 working days. If a mild or moderate adverse event occurs, the principal investigator will summarize the event in the progress report at continuing review.

MONITORING AND QUALITY ASSURANCE

Describe the plan to be followed by the principal investigator/study staff to monitor and assure the validity and integrity of the data and adherence to the IRB-approved protocol. Specify who will be responsible for monitoring, and the planned frequency of monitoring. For example, specify who will review the accuracy and completeness of case report form entries, source documents, and informed consent.

NOTE: Regardless of monitoring plans by the sponsor or others, the principal investigator is ultimately responsible for ensuring that the study is conducted at his/her investigative site in accordance with the IRB-approved protocol, and applicable regulations and requirements of the IRB.

The study staff will routinely review the program "prescription" log as well as all incoming questionnaires for monitoring purposes. Monitoring of the prescription log will also be done by the HDSC staff, as they are the ones who receive and process all requests for SDM programs. Other quality assurance monitoring will be accomplished through the patient and provider questionnaires and interviews. The study staff and the principal investigator will have routine meetings during the study period to ensure the project proceeds as intended per the protocol. We will track recruitment rates and response rates weekly and identify issues as they come up. The study staff will complete all required documents for the study binder and this will be reviewed quarterly by the principal investigator.

The principal investigator will speak with the study staff on a weekly basis and as-needed to ensure that the protocol is being followed. This research does not entail physical risks. We have procedures in place to minimize risks to loss of privacy.

For guidance, refer to the following Partners policies:

Data and Safety Monitoring Plans and Quality Assurance
<http://healthcare.partners.org/phsirb/datasafe.htm>

Adverse Event Reporting Guidelines
<http://healthcare.partners.org/phsirb/adverse.htm>

PRIVACY AND CONFIDENTIALITY

Describe methods used to protect the privacy of subjects and maintain confidentiality of data collected. This typically includes such practices as substituting codes for names and/or medical

record numbers; removing face sheets or other identifiers from completed surveys/questionnaires; proper disposal of printed computer data; limited access to study data; use of password-protected computer databases; training for research staff on the importance of confidentiality of data, and storing research records in a secure location.

NOTE: Additional measures, such as obtaining a Certificate of Confidentiality, should be considered and are strongly encouraged when the research involves the collection of sensitive data, such as sexual, criminal or illegal behaviors.

As the goals of this study are to 1) demonstrate the ability to introduce and disseminate SDM programs to patients, 2) assess and understand “prescribing” utilization, trends and patterns by clinician and across practices, 3) obtain feedback from patients about receiving SDM programs, their decision preferences and comfort with making a decision, and 4) assess the quality of shared decision making for elective surgical decisions.

The study staff will process and manage the distribution and return of programs and questionnaires. Once questionnaires have been returned, the study IDs will be removed so that any ability to link the questionnaires back to patients is removed prior to any review, database entry or analysis of the data. Patient identifiers on the program log (name, address and phone number) will be removed before a copy of it is given to study staff. The study database will not contain any patient information. In this way, the privacy of the subjects and confidentiality of the data collected will be maintained.

No personal information will be captured during the qualitative feedback sessions. Patient privacy will be maintained. All notes will be stripped of any personal identifiers and/or HIPAA related information.

The-interviews will be recorded. The interview data will be identified by a code only. Once the interview is completed, we will not keep the link that ties the participant to the interview. To ensure confidentiality, all study materials will be kept in locked file cabinets and on electronic drives on a Partners password-protected computer to which only the study staff has access.

For the surgery shared decision making survey, study staff will run eCare reports and RPDR queries to gather information on potentially eligible subjects and will review the subject's medical record to confirm eligibility. We will have names and addresses of eligible participants and this information will be kept separate from the study data (e.g. PROMs patient survey data). A separate file on a password-protected Partners shared drive will contain the codes linked to identifying information. Only the MGH study staff and investigators will have access to this file. These will be kept as long as required by the research project. After the study has been completed the personal contact information of all eligible participants will be destroyed.

Cancer Screening Study 2020:

For the cancer screening study, researchers will identify patients who received a decision aid in the HDSC database and will run RPDR queries to gather contact information on potentially eligible subjects and confirm eligibility. We will have names and addresses of eligible participants and this information will be kept separate from the study data (e.g. patient surveys). All patients will receive a code number and the surveys will only be identified by code number. A separate file on a password-protected Partners shared drive will contain the codes linked to identifying information. Only the MGH study staff and investigators will have access to this file. These will be kept as long as required by the research project. After the

study has been completed the personal contact information of all eligible participants will be destroyed.

All paper files (e.g. eligibility screeners) that contain PHI will be kept in a locked file cabinet or in a secure offsite file storage location or on a password protected Partners shared drive.

Patient confidentiality will be maintained as is routine for all patient care privacy guidelines. All research staff are CITI certified and will be trained on the importance of data confidentiality.

SENDING SPECIMENS/DATA TO RESEARCH COLLABORATORS OUTSIDE PARTNERS

Specimens or data collected by Partners investigators will be sent to research collaborators outside Partners, indicate to whom specimens/data will be sent, what information will be sent, and whether the specimens/data will contain identifiers that could be used by the outside collaborators to link the specimens/data to individual subjects.

The de-identified program and decision aid survey data will be shared with the sponsor, the Informed Medical Decisions Foundation. The sponsor is hosting the data warehouse described in detail above and it will aggregate de-identified data from other sites that are funded to collect the same data on implementation of the DVDs/booklets at primary care sites across the country. The data will not contain any identifiers and other investigators, including the sponsor, will not be able to link the data to individual subjects.

A written summary of the interviews that does not contain any personal identifiers will be shared with the Healthwise, who is the funder.

Cancer screening study 2020:

The research team is committed to making resources and data from this proposed research study available to other investigators in the research community. The patient information sheet states the data will be de-identified and made available to others for analysis and research following study completion. The study team will create a clean and de-identified copy of the final data set which will include patient survey data in addition to the limited demographics and cancer screening test. Information for investigators interested in using this data will be made available on the Health Decision Sciences Center website and in publications of the data. [name] will share a de-identified data set with outside investigators at no cost, per approved MGH/Partners policies for data sharing. We will never share the key that will enable an investigator to link the coded data to an individual. Investigators from other sites will be able to request the data and will be required to complete a data use agreement that ensures that all local IRB requirements are met before using the data, that they will not attempt to identify any data in the dataset, and that they will not share the data set with anyone outside their project team. We will also make information necessary to interpret the data, such as study protocols, data dictionaries, and survey tools available to interested investigators.

After the study results have been published, de-identified data sets will also be deposited in an open access service such as, ICPSR (<https://www.icpsr.umich.edu/icpsrweb/>). This is to promote research replicability, transparency and future use of the data. On ICPSR, individuals must register and agree to ICPSR's Responsible Use statement prior to accessing datasets. Additionally, before a dataset is made available for access, ICPSR completes a detailed review of all datasets to assess disclosure risk. If necessary, ICPSR modifies data to reduce disclosure risk or limits access to datasets for which modifying the data would substantially limit their utility or the risk of disclosure remains high. No information that

contains identifiers or that could be used to link an individual to the data will be included in the de-identified data set. The information sheets will contain the following language: *After the study is completed, all identifiable information will be removed from the data and after removal, the de-identified information will be deposited in an open access service to promote use of the data by other researchers.*

Specifically address whether specimens/data will be stored at collaborating sites outside Partners for future use not described in the protocol. Include whether subjects can withdraw their specimens/data, and how they would do so. When appropriate, submit documentation of IRB approval from the recipient institution.

Since there will be no identifying information in the data submitted to the sponsor it will not be possible for an individual to withdraw their information. We have submitted the approval for the protocol held by the sponsor that covers the aggregation of data from MGH and other participating sites.

RECEIVING SPECIMENS/DATA FROM RESEARCH COLLABORATORS OUTSIDE PARTNERS

When specimens or data collected by research collaborators outside Partners will be sent to Partners investigators, indicate from where the specimens/data will be obtained and whether the specimens/data will contain identifiers that could be used by Partners investigators to link the specimens/data to individual subjects. When appropriate, submit documentation of IRB approval and a copy of the IRB-approved consent form from the institution where the specimens/data were collected.

Study staff at MGH will be able to access the aggregated data that the sponsor has collected from other participating sites. MGH study staff will not be able to link data to individual subjects from other participating sites. We have attached the IRB approval held by the sponsor that covers the aggregation of data from MGH and the other participating sites.

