3. Clinician “prescribes” program through the electronic medical record, and gives patient the one-page description of the program that automatically prints when the program is ordered. The “prescription” function in the electronic medical record triggers an email message with the order information to be sent to the Blum Patient and Family Learning Center.
4. The program is sent (or given, in the case of the “pick-up” option) to the patient with a questionnaire and pre-paid, addressed envelope. The goal of the questionnaire is to assess the patient’s intentions with regard to the topic and the patient’s opinion about shared decision-making prior to viewing the decision aid. After viewing the decision aid, patients will also be asked a series of general knowledge questions about the target topic and a few questions evaluating the content and comprehensiveness of the decision aid itself.
5. Some patients will receive a follow-up “post-visit” survey in the mail and a pre-paid addressed envelope several months after receiving a decision aid. The purpose of this questionnaire is to learn the extent to which viewing decision aids impacts patients’ conversations with their providers and ultimately their treatment decisions.

It is difficult to anticipate the total number of patients who will receive a SDM program because the “prescription” of the program is incorporated into routine clinical care, similar to clinicians giving a pamphlet or other written patient education materials to their patients. We anticipate the target enrollment of patients to be 80,000. Patients who are eligible are:

- Adult patients in the Partners Healthcare System primary or specialty care practices.
- Patients, for whom a SDM program is clinically appropriate, based on the clinical judgment of the clinician. This includes patients with the following health

problems/concerns: general healthcare options, low back pain (chronic, acute, spinal stenosis, and herniated disc), osteoarthritis of the knee or hip, coronary artery/heart disease, benign prostatic hyperplasia, abnormal uterine bleeding, uterine fibroids, symptoms of menopause, obesity, depression, ovarian cancer screening, prostate cancer screening, colorectal cancer screening, advance directives, heart failure, diabetes, breast cancer treatment, prostate cancer treatment, insomnia, carotid artery disease, and chronic pain.

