- Once questionnaires have been returned, a study staff will enter the coded de-identified data into a secured online data warehouse separate from the information crosswalk with no ability to link the data back to patient's personal and HIPAA related information.

The providers' perspectives will also be collected, periodically, through questionnaires or individual interviews. An email invitation will be sent to all eligible Partners Healthcare System primary care physicians, specialists, nurses and other clinic staff involved in a patient's care to complete either the questionnaire or participate in an interview. The providers and staff will be able to choose to complete the questionnaire online or by paper. A reminder email will be sent to those who haven't completed the questionnaire within a 2-week timeframe. Study staff will work individually with those interested in the interviews, at the time of a specific project.

Patients who have indicated their consent to be contacted in the future for other studies will be contacted to see if they would be interested in participating in a pilot study examining the effectiveness of mental health decisions aids: sleeping better, depression, and anxiety. Patients will be contacted first by telephone and asked if they would be interested in participating in a survey study. If they agree to participate they will be asked to review some additional patient educational materials either online or on paper. After the patient reviews the materials, they will be asked to complete and answer the questions via phone with study staff at a scheduled time. Consent will be implied by the completion of the questionnaire. If a patient would like to complete the questionnaire via paper, an information sheet, questionnaire, and return-envelope will be sent to the patient. The project goal is to have approximately 30 eligible patients complete the survey.

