Patients who have indicated their consent to be contacted in the future for other studies will be contacted to see if they would be interested in participating in a pilot study examining the effectiveness of mental health decisions aids: sleeping better, depression, and anxiety. Patients will be contacted first by telephone and asked if they would be interested in participating in a survey study. If they agree to participate they will be asked to review some additional patient educational materials either online or on paper. After the patient reviews the materials, they will be asked to complete and answer the questions via phone with study staff at a scheduled time. Consent will be implied by the completion of the questionnaire. If a patient would like to complete the questionnaire via paper, an information sheet, questionnaire, and return-envelope will be sent to the patient. The project goal is to have approximately 30 eligible patients complete the survey.

Patients who have indicated their consent to be contacted in the future for other studies will be contacted to see if they would be interested in participating in a structured interview either in-person or via telephone to learn more about decision making for older adults about whether to continue colorectal cancer screening. We may also have primary care physicians (PCP) identify patients who they believe would good candidates to participate in the interviews. The PCP will provide the patient with the information sheet and if the patient is interested, the PCP will provide the research staff contact information for the subject to call to indicate their interest in participating. Subjects will be contacted first by telephone and asked their interest to participate in an interview. If they agree to participate they will be asked whether they prefer to conduct the interview in-person or via telephone and study staff will schedule a mutually convenient time. Consent will be implied by the completion of the interview. A cover letter and an information sheet will be sent by mail or email (if subjects provide verbal consent to use personal email) for those interested in an interview. All emails that are sent for recruitment will be sent in accordance with Partners' institutional guidelines for information security. The project goal is to have approximately 20 eligible subjects complete the interview.

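### The mental-health decision-aid pilot aims to examine effectiveness, but its phone procedure measures patients only after review, so it gives no measured change or contrast attributable to the aids

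*Combined protocol and SAP*

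**What the plan says.** The pilot is described in the same terms under Research Design and Methods and under Recruitment Procedures.

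- **Purpose:** a "pilot study examining the effectiveness of mental health decisions aids", on three topics (sleep, depression and anxiety).
- **Exposure:** patients who earlier agreed to re-contact are telephoned. "If they agree to participate they will be asked to review some additional patient educational materials either online or on paper". No one is assigned to anything else.
- **Measurement, phone route:** "After the patient reviews the materials, they will be asked to complete and answer the questions via phone with study staff at a scheduled time".
- **Measurement, paper route:** "If a patient would like to complete the questionnaire via paper, an information sheet, questionnaire, and return-envelope will be sent to the patient". The order of questionnaire and review is not stated.
- **Size:** "The project goal is to have approximately 30 eligible patients complete the survey". No split over the three topics is given.

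Neither section names an outcome, an effect measure, a reference value or an analysis for this pilot.

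**The concern.** Effectiveness is a claim about a difference: after against before, or with the aid against without it. On the phone route the plan supplies only the *after*, in a single group. A favourable post-review score could then be the level patients already had.

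The recruitment source makes this more than a formality. Permission for re-contact is collected from people who have already received a decision aid or a study survey, and the pilot materials are described as additional ones. Some participants may therefore start well informed or already comfortable with shared decisions. The risk is that post-review scores are later reported as evidence that the aids work.

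**Working it through.** **1. Is a contrast supplied elsewhere in the protocol?** Two places could supply one.

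- *Pre-viewing questions.* For programs prescribed in routine care, the questionnaire has a part completed before the aid is seen: "The goal of the questionnaire is to assess the patient’s intentions with regard to the topic and the patient’s opinion about shared decision-making prior to" […]. Further questions come afterwards. The reminder procedures also separate pre-viewing from post-viewing questions. All of this concerns the questionnaire sent with prescribed programs. The pilot has its own sequence, and nothing says that it uses that instrument.
- *Recipients and non-recipients.* The medical chart abstraction covers both, but it concerns visits, testing and treatment decisions. It is not linked to the pilot or its questionnaire.

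Neither is tied to the pilot.

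**2. The plan's own figure.** The target of about 30 cannot be reproduced. No significance level, power, effect size, standard deviation, precision target or outcome is given. It is a recruitment goal, not a power claim.

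**3. What one post-review measurement estimates.** Write the post-review mean as (pre-review mean) + (change). The data estimate only the sum. Any starting level, paired with the matching change, fits equally well, whatever the sample size. A between-group difference needs a second group, and none is planned.

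**4. Precision of what can be described.** The 95% level and the even split of 30 / 3 = 10 per topic are assumptions.

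| | n = 30 | n = 10 (one topic) |
|---|---|---|
| Exact 95% CI, observed 50% | 31% to 69% | 19% to 81% |
| Exact 95% CI, observed 80% | 61% to 92% | 44% to 97% |
| Half-width for a mean, t(0.975, n−1)/√n | 0.37 SD | 0.72 SD |

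**5. What a pre-review measure would add.** Assumed: two-sided 5%, 80% power, paired t-test.

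- Normal approximation, 30 pairs: (1.960 + 0.842)/√30 = 0.51. The exact noncentral-t value is 0.53.
- Normal approximation, 10 pairs: 2.802/√10 = 0.89. The exact value is 1.00.

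The unit is the SD of the *within-patient change*. This equals the SD of the score only if the pre-post correlation is 0.5, because SD of change = SD × √(2(1 − ρ)). The 95% half-width for the pooled mean change is 0.37 of the same unit.

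**6. Splitting the 30 into two arms instead.** With 15 per arm the detectable difference is 2.802 × √(2/15) = 1.02 SD. Power is about 28% for 0.5 SD and 59% for 0.8 SD (normal approximation). A comparison group within the same 30 would therefore detect only large differences.

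**The case against.** The strongest reply has four parts.

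- **A post-only survey is not empty.** The third specific aim seeks feedback on the effect of a program on decision preference, and Consent Procedures lists helpfulness and effect on preference among the questionnaire topics. Patients can report perceived effect in one sitting. This stands. A reader might infer that the pilot can say nothing at all about effect, and the documents do not support that. What is missing is a measured change or contrast.
- **The missing baseline is an inference from silence.** The pilot's questionnaire is not reproduced, and the paper route fixes no order. This stands as a limit. The post-review timing is explicit for the phone route only.
- **It is a small pilot with loose wording.** None of the protocol's aims or endpoints concerns the effectiveness of mental-health aids. This stands in part: nothing central depends on the pilot. But the purpose is stated in two sections, and a pilot should still not claim a purpose that its data cannot serve. A reader might also infer that 30 patients is an underpowered sample. That does not follow, because no power is claimed.
- **A before-after change is not effectiveness either.** It has no control, repeated items may prime patients, the baseline may follow an earlier decision aid, and topic-specific knowledge items do not pool. All of this stands. It limits what the repaired pilot may claim and restricts the pooled items to those common across topics.

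**Conclusion.** The point holds in a limited form. The purpose stated in both sections goes beyond what the described procedure can deliver. The phone route gives post-review levels, acceptability and self-reported helpfulness, but no measured change or contrast attributable to the aids. That conclusion rests on the stated sequence and on the absence of any pre-review measure or comparison group tied to the pilot. It does not depend on the number of patients.

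The numerical results are illustrative, since the significance level, power and split by topic are assumptions. They show that only a pooled change would be reasonably informative with 30 patients: about 0.53 SD of the within-patient change is detectable, against about 1.0 SD within a topic of 10. Even then the result is a preliminary before-after estimate. The mismatch is worth correcting, but it does not touch the main endpoints.

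**What to change.** **Preferred change.** After the patient agrees and before the materials are sent, ask a short set of core items common to all three topics, for example decision certainty or preference, on the recruitment call already planned. On the paper route, place the same items before the review. Repeat them afterwards. Report the pooled within-patient change with a confidence interval, labelled a preliminary, uncontrolled before-after estimate. Keep topic-level results and topic-specific knowledge descriptive.

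**Consent.** Amend the call script and information sheet so that implied consent covers the pre-items. The pilot's own description mentions the information sheet only for the paper route, although Consent Procedures provides one to re-contacted patients generally. Its timing relative to the pre-items should be stated.

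**Cost.** A few minutes on an existing call, a minor amendment and no extra patients. The drawbacks are slight extra burden, possible priming, and a baseline that may not be free of earlier decision-aid exposure. Recording earlier receipt from the program log would make that last limit visible.

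**Alternative.** If pre-items are not added, replace *effectiveness* with *acceptability and perceived helpfulness* under both Research Design and Methods and Recruitment Procedures. This costs only the wording change.
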